3.0 Inclusion and Exclusion Criteria

3.1 Inclusion Criteria

- Adults aged 18-70
- Shoulder pain lasting at least 4 weeks
- Inability to use arm with restriction of movement and loss of full function.
- Able to understand study and provide voluntary, written informed consent

3.2 Exclusion Criteria

- Less than 18 or greater than 70 years old
- Contraindications of previous injections and previous shoulder surgery
- Unable to understand consent form (in the opinion of the PI)
- Non-English speaking individuals
- Medication contradictions to lidocaine, corticosteroids

3.3 Early Withdrawal of Subjects

3.3.1 Criteria for removal from study

Patients will be withdrawn from the study for safety reasons including severe adverse reactions, failure of subject to adhere to protocol requirements, or subject consent withdrawal.

3.3.2 Follow-up for withdrawn subjects

The subjects may withdraw at any point prior to the steroid injection. Additionally, they may elect not to participate in rating their pain right after they receive the injections. Subjects who withdraw and prefer to have a lidocaine injection, may still participate in rating their pain after the lidocaine + steroid injection. Any subject who is getting steroid injections for shoulder pain may replace subjects who withdrew.

4.0 Recruitment Methods

4.1 Identification of subjects

Subjects will be identified as part of their initial or routine evaluation by one of the study investigators in the Bone & Joint Institute.

4.2 Recruitment process

If steroid injections are indicated for subjects with shoulder pathologies who come to the Orthopedics department, they will be asked to participate in the study.

4.3 Recruitment materials

Not applicable.

4.4 Eligibility/screening of subjects

Adult patients presenting to the Bone & Joint Institute will be evaluated as part of standard of care. Those subjects meeting eligibility requirements will be presented with the opportunity to participate in the research study by a member of the research team.

5.0 Consent Process and Documentation

5.1 Consent Process

5.1.1 Obtaining Informed Consent

5.1.1.1 Timing and Location of Consent

Subjects presenting to the study investigator's practice site as part of their initial or routine evaluation will be given the opportunity to participate in the research study. Patients will be given information about the study and asked to participate. If eligible, based on inclusion and exclusion criteria, informed consent will be obtained at the time of the screening visit and the patient will be enrolled in the study.

5.1.1.2 Coercion or Undue Influence during Consent

Subjects will be given ample time to read and review the consent form on their own. All questions the patient may have will be answered and written consent will be obtained. A member of the research team will assist in the explanation and obtaining of the written consent. A copy of the signed consent will be given to the patient and another copy sent to Medical Records. Subjects will be informed they do not have to participate in this research study. They will be informed that their current and future care at the PSHMC will not be affected by their decision to accept or decline participation.

5.1.2 Waiver or alteration of the informed consent requirement

Requesting a waiver to screen for eligibility prior to the informed consent document being signed.

5.2 Consent Documentation

5.2.1 Written Documentation of Consent

A member of the research team will assist in the explanation and obtaining of the written consent. A copy of the signed consent will be given to the patient and another copy sent to Medical Records.

5.2.2 Waiver of Documentation of Consent (Implied consent, Verbal consent, etc.)

Not applicable.

5.3 Consent – Other Considerations

5.3.1 Non-English Speaking Subjects

Not applicable.

5.3.2 Cognitively Impaired Adults

5.3.2.1 Capability of Providing Consent

Not applicable.

5.3.2.2 Adults Unable To Consent

Not applicable.

5.3.2.3 Assent of Adults Unable to Consent

Not applicable.

5.3.3 Subjects who are not yet adults (infants, children, teenagers)

5.3.3.1 Parental Permission

Not applicable.

5.3.3.2 Assent of subjects who are not yet adults

Not applicable.

6.0 HIPAA Research Authorization and/or Waiver or Alteration of Authorization

6.1 Authorization and/or Waiver or Alteration of Authorization for the Uses and Disclosures of PHI

Check all that apply:

- Not applicable, no identifiable protected health information (PHI) is accessed, used or disclosed in this study. [Mark all parts of sections 6.2 and 6.3 as not applicable]
- Authorization will be obtained and documented as part of the consent process. [If this is the only box checked, mark sections 6.2 and 6.3 as not applicable]
- Partial waiver is requested for recruitment purposes only (Check this box if patients' medical records will be accessed to determine eligibility before consent/authorization has been obtained). [Complete all parts of sections 6.2 and 6.3]
- Full waiver is requested for entire research study (e.g., medical record review studies). [Complete all parts of sections 6.2 and 6.3]
- Alteration is requested to waive requirement for written documentation of authorization (verbal authorization will be obtained). [Complete all parts of sections 6.2 and 6.3]

6.2 Waiver or Alteration of Authorization for the Uses and Disclosures of PHI

6.2.1 Access, use or disclosure of PHI representing no more than a minimal risk to the privacy of the individual

6.2.1.1 Plan to protect PHI from improper use or disclosure

Information is included in the "Confidentiality, Privacy and Data Management" section of this protocol.

6.2.1.2 Plan to destroy identifiers or a justification for retaining identifiers

The list will be destroyed upon completion of the study.

6.2.2 Explanation for why the research could not practicably be conducted without access to and use of PHI

Patient identifiers are necessary for identification and review of the patient's medical records. A unique study code number will be used for identification of study data. The linking list will be destroyed upon completion of the study.

6.2.3 Explanation for why the research could not practicably be conducted without the waiver or alteration of authorization

Waiver is required to screen for eligibility.

6.3 Waiver or alteration of authorization statements of agreement

Protected health information obtained as part of this research will not be reused or disclosed to any other person or entity, except as required by law, for authorized oversight of the research study, or for other permitted uses and disclosures according to federal regulations.

The research team will collect only information essential to the study and in accord with the 'Minimum Necessary' standard (information reasonably necessary to accomplish the objectives of the research) per federal regulations.

Access to the information will be limited, to the greatest extent possible, within the research team. All disclosures or releases of identifiable information granted under this waiver will be accounted for and documented.

7.0 Study Design and Procedures

7.1 Study Design

The trial is a randomized, prospective study. Patients undergoing steroid injections will be randomized into three groups:

- Group A=Injection of 1 ml of 40 mg Kenalog combined with 4 ml of 1% lidocaine
- Group B=Injection of 1 ml of 40 mg Kenalog combined with 4 ml of 1% lidocaine after 2 ml in subcutaneous injection
- Group C=Injection of 1 ml of 40 mg Kenalog combined with 4 ml of 1% lidocaine after applying ethyl chloride spray for 3 seconds

Patients' pre and post-procedural pain as well as the pain of the injection itself will be assessed with a visual pain scale and the results will be analyzed for statistical significance.

7.2 Study Procedures

The study consists of one visit in clinic during their standard of care visit. Patients will be given information about the study and asked to participate. If eligible, based on inclusion and exclusion criteria, informed consent will be obtained at the time of the screening visit and the patient will be enrolled in the study.

After obtaining informed consent, the patient will be asked to rate their current pain on a visual 1-10 point scale before injection. They will then be randomized to one of three treatment groups. The study investigator will randomly draw a sealed envelope containing one of the three treatment groups. The sealed envelopes will be stored in a secure area within the clinic practice site. The subject will be randomized to one of three groups:

- Group A=Injection of 1 ml of 40 mg Kenalog combined with 4 ml of 1% lidocaine
- Group B=Injection of 1 ml of 40 mg Kenalog combined with 4 ml of 1% lidocaine after 2 ml in subcutaneous injection
- Group C=Injection of 1 ml of 40 mg Kenalog combined with 4 ml of 1% lidocaine after applying ethyl chloride spray for 3 seconds

The needle size will be standardized:

- 25 gauge needle for the subcutaneous lidocaine injection
- 21 gauge needle for the combined injection

Immediately after and ten minutes after the injection is completed, they will also be asked to rate pain on the same 1-10 visual scale.

No long-term follow-up will be conducted.

7.3 Duration of Participation

The subject will only be participating from the time they receive the injection to when they indicate the level of pain on the pain scale; i.e. they will be seen in the clinic site once.

7.4 Test Article(s) (Study Drug(s) and/or Study Device(s))

7.4.1 Description

All of these drugs and listed dosages are currently FDA approved and considered standard of care.

Lidocaine hydrochloride injection: USP is sterile, nonpyrogenic, aqueous solution that contains a local anesthetic agents and is administered parenterally by injection. It is FDA approved and indicated for production of local or regional anesthesia by infiltration techniques such as steroid injections

Ethyl Chloride spray: a vapocoolant (skin refrigerant) intended for topical application to control pain associated with injections. It is FDA approved.

Kenalog Injection (triamcinolone acetonide): a synthetic glucocorticoid corticosteroid with anti-inflammatory action. This formulation is FDA approved for intramuscular and intra-articular use only

7.4.2 Treatment Regimen

- Group A=Injection of 1 ml of 40 mg Kenalog combined with 4 ml of 1% lidocaine
- Group B=Injection of 1 ml of 40 mg Kenalog combined with 4 ml of 1% lidocaine after 2 ml in subcutaneous injection
- Group C=Injection of 1 ml of 40 mg Kenalog combined with 4 ml of 1% lidocaine after applying ethyl chloride spray for 3 seconds

7.4.3 Method for Assigning Subject to Treatment Groups

The subjects will be randomized by drawing a treatment group from a sealed envelope.

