7.4.5 Blinding of the Test Article

Not applicable.

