7.4.6.3 Preparation and Dispensing

The study drug will be prepared by an investigator following standard of care protocols. Subject randomization will be performed prior to dispensing of any study drugs. Once the needle is in the proper location, the solution of steroid will be injected slowly. A 2 mL solution of 1% lidocaine without epinephrine will be injected subcutaneously prior to the steroid injection if the subject is randomized into group B. If subject is in group C, ethyl chloride spray will be applied for 3 seconds prior the steroid injection.

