16.2 Feasibility of recruiting the required number of subjects

The Penn State Hershey Bone and Joint Institute cares for many patients with shoulder problems that need to get steroid injections to relieve pain. The PI does 1-2 injections per clinic and has 2 clinics a week. After 52 weeks the sample size would be around 150, which is above the 138 subject sample size calculated by the edited stats analysis.

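### The investigator draws freely from unnumbered sealed envelopes, so in this unblinded trial an unwanted allocation could be redrawn and would be hard to detect

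*Combined protocol and SAP*

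**What the plan says.** Section 7.2 carries the operative statement: "The study investigator will randomly draw a sealed envelope containing one of the three treatment groups". On custody it says: "The sealed envelopes will be stored in a secure area within the clinic practice site". Section 7.4.3, the section on assignment, says only: "The subjects will be randomized by drawing a treatment group from a sealed envelope".

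The order of events in section 7.2 is consent, then the baseline pain rating, then the draw. Pain is rated again by the patient immediately after the injection and ten minutes later. Section 7.4.5, on blinding, reads "Not applicable", and section 19.6 on unblinding says the same.

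Section 8.3 analyses change in pain by one-way ANOVA with indicators for study group and nothing else. Section 3.3.2 foresees that some patients will withdraw because they prefer a lidocaine injection. It allows withdrawn patients to be replaced, without saying which allocation the replacement receives.

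**The concern.** Drawing an envelope at random is a stated mechanism, and it differs in kind from opening the next envelope in a numbered series. In a numbered series, a skipped or substituted envelope breaks the order and shows up on reconciliation. In a free draw any sealed envelope is as proper as any other, so there is no order to check. The protocol also gives no number of envelopes per arm, no record tying an envelope to a patient, and no custodian outside the study team.

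What is at stake is the comparison of arms. There is no blinding and the endpoint is the patient's own rating, so the integrity of the allocation carries most of the protection against bias. The person drawing can know the baseline score and may know what the patient hopes to receive. If a few draws are repeated on either ground, the arms differ in expected change before any treatment effect. A group-only ANOVA has no term that would absorb a resulting imbalance in baseline pain.

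**Working it through.** **1. The plan's own figure.** Section 8.2 gives a difference of 2 points, SD 3, a type I error of 1.7% (0.05/3) per comparison, 80% power and 50 per group. Sidedness is not stated; two-sided is assumed. The standard error of a difference is 3 × √(2/50) = 0.6. The exact two-sample t-test gives 81.3% power at 50 per arm and first reaches 80% at 49 per arm (80.4%). The stated size reproduces, and nothing below alters it.

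**2. Who does what.**
- Identification (4.1): "Subjects will be identified as part of their initial or routine evaluation by one of the study investigators in the Bone & Joint Institute".
- Approach to eligible patients (4.4): they are "presented with the opportunity to participate in the research study by a member of the research team".
- Draw (7.2): the study investigator.
- Preparation (7.4.6.3): "The study drug will be prepared by an investigator following standard of care protocols".
- Injection: the recruitment estimate in 16.2 rests on the principal investigator's own practice, "The PI does 1-2 injections per clinic and has 2 clinics a week".

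The roles may overlap. No section says that one person fills them all, and no section separates the draw from the clinical roles.

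**3. How far one redraw moves an allocation.** Assume a large set of envelopes with equal numbers per arm. One draw reaches a preferred arm with probability 1/3. If one unwanted draw can be put back, the probability is 1/3 + (2/3)(1/3) = 5/9, and each other arm has 2/9.

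**4. Bias from one redraw.** Assume a fraction q of patients differ from the rest by 3 points (1 SD) in expected change and are redrawn once toward arm X when the first draw is another arm. Let Y be one of the other arms.
- Share of such patients in X: (5q/9) / [5q/9 + (1 − q)/3].
- Share in Y: (2q/9) / [2q/9 + (1 − q)/3].
- Bias = 3 × (share in X − share in Y).

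| q | Share in X | Share in Y | Bias (points) | Bias ÷ 2-point target |
|---|---|---|---|---|
| 5% | 0.0806 | 0.0339 | 0.14 | 7% |
| 10% | 0.1563 | 0.0690 | 0.26 | 13% |
| 20% | 0.2941 | 0.1429 | 0.45 | 23% |

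**5. Effect on one pairwise test.** By normal approximation with standard error 0.6 and a two-sided critical value of 2.394, the bias in standard-error units is 0.23, 0.44 and 0.76. The false-positive rate rises from 1.7% to about 2.0%, 2.7% and 5.2%. These rates are for one pairwise test taken alone and ignore the overall F-test that comes first in section 8.3.

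**6. Range under other assumptions.** Suppose expected change is normal with SD 3, is perfectly foreseen, and steering always succeeds, sending patients above the mean to one arm and those below it to another. The gap between the halves is 2 × √(2/π) × 3 = 2 × 0.798 × 3 = 4.8 points, and q × 4.8 gives 0.24, 0.48 and 0.96 points. If foresight correlates only 0.3 with outcome, these become 0.07, 0.14 and 0.29.

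**7. Arm sizes.** The protocol does not say that a fixed 50/50/50 set of envelopes is prepared. If allocation is in effect simple randomisation of 150, the smallest arm has a median of about 45 (2.5th percentile 36), not 50.

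**The case against.** The strongest reply is that the protocol never permits an envelope to be returned or redrawn, and that doing so would breach the random draw it prescribes. On this view the complaint is about unreported detail. The envelopes are sealed and securely stored, which limits foreknowledge, and consent and the baseline rating already come before the draw. All of that stands. It does not answer the point, because sealing and storage act before an envelope is opened and a redraw happens after. That the envelopes form a pool is an inference, but it is the natural reading of a random draw from several stored envelopes. Section 9.0 refers to a separate form for data management; nothing suggests that it covers allocation.

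A reader might infer three stronger things that the documents do not support:
- **That steering would leave no trace.** Baseline pain is recorded before the draw, so steering on it could show as baseline imbalance. A broken seal is some evidence, and counts could be reconciled if a fixed set was made. Steering on unrecorded preference is the harder case to see.
- **That one person identifies, enrols, draws and injects.** Section 4.4 lets any research team member present the study, and the other sections do not name a single individual.
- **That a bias of 0.24 to 0.96 points is to be expected.** Those figures treat the whole outcome SD as foreseeable and every attempt to steer as successful. They are an upper-end case.

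**Conclusion.** The point holds as a weakness in the stated allocation method: a free draw by an investigator, with no numbering, independent sequence or log, leaves room for a redraw that would be hard to detect. It does not suggest that anyone would misuse the procedure.

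The one-redraw figures are the most reasonable illustration of size. They rest on a large, equal set of envelopes, a 3-point difference in expected change for the redrawn patients, and redraw rates that appear nowhere in the documents. The bias is modest against the target difference, but at a 20% redraw rate it roughly triples the error rate of a single pairwise test.

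The direction cannot be stated in advance. Steering patients with high baseline scores to one arm could exaggerate its benefit through regression to the mean. Steering patients who expect a painful injection toward skin anaesthesia could hide a benefit. This is a change that should be made because it is cheap and because concealment cannot be restored once patients are enrolled.

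**What to change.** In sections 7.2 and 7.4.3, replace the random draw with the following:
- A computer-generated 1:1:1 list, for example in permuted blocks of varying size giving 50 per arm, prepared by someone who does not enrol or inject, such as a study statistician. The protocol identifies no such person, so one must be named.
- Opaque, sealed, sequentially numbered envelopes, opened strictly in order, and only once consent and the baseline rating are recorded.
- Subject code, date and time written on the envelope before it is opened. An opened envelope is never returned or reused.
- An allocation log reconciled against the envelopes, including those of withdrawn patients. A patient who replaces a withdrawal takes the next unused number.
- Where possible, a team member other than the injecting investigator opens the envelope.

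The cost is a small amount of preparation time, brief record-keeping per patient and a wording change. Treatments, visits and sample size are unaffected.

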7.4.4 Subject Compliance Monitoring

Subject compliance monitoring is not necessary as there will only be 1 treatment protocol for this study.

7.4.5 Blinding of the Test Article

Not applicable.

7.4.6 Receiving, Storage, Dispensing and Return

7.4.6.1 Receipt of Test Article

The compounds are used in the Bone & Joint Institute as standard of care.

7.4.6.2 Storage

The compounds will be stored at room temperature in the Bone & Joint Institute as per standard of care instructions.

7.4.6.3 Preparation and Dispensing

The study drug will be prepared by an investigator following standard of care protocols. Subject randomization will be performed prior to dispensing of any study drugs. Once the needle is in the proper location, the solution of steroid will be injected slowly. A 2 mL solution of 1% lidocaine without epinephrine will be injected subcutaneously prior to the steroid injection if the subject is randomized into group B. If subject is in group C, ethyl chloride spray will be applied for 3 seconds prior the steroid injection.

7.4.6.4 Return or Destruction of the Test Article

The study drug will be disposed of in clinic following standard procedure for disposal of needles.

7.4.6.5 Prior and Concomitant Therapy

No prior and concomitant therapy will be collected.

8.0 Subject Numbers and Statistical Plan

8.1 Number of Subjects

Approximately 150 subjects (50 per treatment arm).

8.2 Sample size determination

The primary endpoint is the change in visual pain scale from baseline (pre-injection) to follow up (0- and 10-minutes after injection). The study contains 3 groups:

- Group A=Injection of 1 ml of 40 mg Kenalog combined with 4 ml of 1% lidocaine
- Group B=Injection of 1 ml of 40 mg Kenalog combined with 4 ml of 1% lidocaine after 2 ml in subcutaneous injection
- Group C=Injection of 1 ml of 40 mg Kenalog combined with 4 ml of 1% lidocaine after applying ethyl chloride spray for 3 seconds

Comparisons will be made for the primary outcome between all 3 study groups: Group B vs. A; Group C vs. A; and Group C vs. B. Thus, we used a Bonferroni corrected Type I error rate for 3 tests to determine the sample size required for 80% power.

A total of N=50 patients per group (N=150 total) yields 80% power for a t-test conducted at the Bonferroni corrected Type I error rate of 1.7%, which holds the overall Type I error rate for the study at 5%, to detect a 2-point difference in pain scale changes between groups, assuming a common standard deviation of 3 points. The standard deviation was calculated after making a conservative assumption that visual pain scores would be uniformly distributed across 0-10.

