1.2 Primary Study Endpoints

The primary endpoint is to determine whether local anesthetics prior to subacromial injections reduce pain, quantified on a 1-10 pain scale.

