1.3 Secondary Study Endpoints

Not applicable

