8.3 Statistical methods

A one-way analysis of variance (ANOVA) model will be used to test whether changes in pain scores differ by study group. The outcome variable for the model will be the change in pain scores, and the independent variables will be indicators of each study group. The overall F-test for study group will be used to determine whether study groups differ with respect to mean changes in visual pain scores. If the F-test is significant, then follow up tests comparing each set of groups will be conducted using the Bonferroni-adjusted Type I error rate of 1.7%.

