10.7 Statistical tests

A one-way analysis of variance (ANOVA) model will be used to test whether changes in pain scores differ by study group. The outcome variable for the model will be the change in pain scores, and the independent variables will be indicators of each study group. The overall F-test for study group will be used to determine whether study groups differ with respect to mean changes in visual pain scores. If the F-test is significant, then follow up tests comparing each set of groups will be conducted using the Bonferroni-adjusted Type I error rate of 1.7%.

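### Section 8.2 makes the change at both 0 and 10 minutes primary but sets 1.7% for three group comparisons at one time, and no section says which change is analysed, so the 5% depends on a rule not yet written

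*Combined protocol and SAP*

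**What the plan says.** Section 7.2 schedules two ratings after the injection: "Immediately after and ten minutes after the injection is completed, they will also be asked to rate pain on the same 1-10 visual scale". Section 8.2 makes both primary: "The primary endpoint is the change in visual pain scale from baseline (pre-injection) to follow up (0- and 10-minutes after injection").

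The same section lists three comparisons (B with A, C with A, C with B) and continues: "Thus, we used a Bonferroni corrected Type I error rate for 3 tests to determine the sample size required for 80% power". It gives the level as 1.7%, "which holds the overall Type I error rate for the study at 5" per cent.

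The analysis model in 8.3 has one outcome: "The outcome variable for the model will be the change in pain scores, and the independent variables will be indicators of each study group". Section 10.7 repeats it: "The outcome variable for the model will be the change in pain scores". The overall F-test comes first, and pairwise tests at 1.7% follow only if it is significant.

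The endpoint sections do not order the two times. Section 1.2 says "The primary endpoint is to determine whether local anesthetics prior to subacromial injections reduce pain, quantified on a 1-10 pain scale", with no time, and the entry under 1.3 for secondary endpoints is "Not applicable".

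**The concern.** A one-way ANOVA needs one number per patient, and the plan supplies two. Two analysts could both follow 8.3 to the letter, one using the 0-minute change and the other the 10-minute change, and report different primary results. The two results would also mean different things: less pain around the procedure, or less pain ten minutes later.

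The error rate is tied to the same gap. The correction counts three tests, but three comparisons at each of two times make six. Whether the stated 5% is true depends on how the two times are used, and the stated 80% power depends on it as well.

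**Working it through.** **Inputs.** From 8.2: 50 per group, a difference of 2 points, SD 3, 1.7% per comparison, 5% overall, 80% power. From 8.3: F-test first, then pairwise tests at 1.7%. Three inputs are not in the documents and are assumed: two-sided tests, the F-test at 5%, and a correlation of 0 to 0.9 between the two changes.

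**Step 1: the plan's own figure.** 0.05 / 3 = 0.0167, which rounds to 1.7%. For a two-sample t-test the noncentrality is 2 / (3 × √(2/50)) = 2 / 0.6 = 3.33 on 98 degrees of freedom. Power is 81.3% at 0.0167 and 81.5% at 0.017, and 80% is reached with 49 per group. So 50 per group and 80% reproduce, for three comparisons at one time. A one-sided test would need only 40 per group, so two-sided is the reading that fits.

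**Step 2: simple bounds if either time can count.** There are 3 × 2 = 6 pairwise tests. The Bonferroni bound is 6 × 0.0167 = 10%. The tests are correlated and gated by the F-test, so the true rate is lower.

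**Step 3: simulated rate if either time can count.** Three groups of 50, normal changes, no true difference at either time, 100,000 trials per correlation:

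| Correlation | Either F-test significant | False gated pairwise claim, two-sample t | Same, pooled variance |
|---|---|---|---|
| 0 | 9.8% | 8.0% | 8.3% |
| 0.5 | 9.0% | 7.5% | 7.7% |
| 0.7 | 8.5% | 6.9% | 7.2% |
| 0.9 | 7.1% | 5.9% | 6.1% |

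**Step 4: which correlations are plausible.** Both changes subtract the same baseline. Suppose the three ratings have equal variance s² and a common correlation c. The covariance of the two changes is cs² − cs² − cs² + s² = s²(1 − c), and each variance is 2s²(1 − c), so the correlation is 0.5 whatever c is. A value near 0 would need the two later ratings to be clearly less related to each other than to baseline. For 0.5 to 0.9 the false pairwise claim rate is about 6-7.7%.

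**Step 5: the other rules.**
- One time fixed in advance: false gated pairwise claim 4.0-4.3%; power for 2 points with the F gate about 81-82%.
- Average of the two times fixed in advance: 4.0-4.3%.
- Both times significant for the same pair: at most 4.3%, the worst case being a real effect at one time only. Power for 2 points at both times is about 66-77%.

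**Step 6: an either-can-count rule that holds 5%.** Put the F-test at 2.5% per time and keep pairwise tests at 1.7%.
- No differences at either time: a false claim needs an F-test to reject, so at most 2.5% + 2.5% = 5% (simulated 3.6-5.0%).
- One group different at both times: one true null pair per time, so at most 1.7% + 1.7% = 3.4%.
- One group different at one time only: at most 1.7% + 2.5% = 4.2%.

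Power for a 2-point pair at any one named time is about 76% with the third group midway, and about 80% with the third group equal to one of the pair. If the 2 points are present at both times, the chance of detecting them at one or both is about 81% or more.

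**The case against.** The strongest reply is that the plan describes one analysis. Section 8.2 speaks of one primary endpoint and three tests, and 8.3 has one outcome, one model and one overall F-test. On that reading 1.7% is correct and only a label is missing. Some text also leans towards 0 minutes: 2.1 mentions discomfort during and straight after the procedure, 3.3.2 describes rating pain right after the injection, and 7.1 lists the pain of the injection itself.

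Much of this stands. No section says that either time may count, so a breach of 5% is conditional on a rule the plan never states. The inflation is modest, and the highest figures need a correlation of 0. It also belongs mainly to the case of no differences anywhere. With one group truly 2 points apart at both times, the unadjusted rule gives a false claim for the remaining pair in roughly 2-3.4% of trials. With the effect at one time only, it is about 4.8-5.7%.

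What does not stand is that the reply settles the matter. A single outcome is implied, but no section says which one. Section 8.2 names both times outright, and 2.3 frames the question around the pain relief given by the steroid, which does not point to 0 minutes.

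**Conclusion.** The concern holds as a gap in the definition of the primary analysis, and it needs to be closed before any group results are seen. The primary analysis cannot be run as written without an unplanned choice. The stated 5% is true under some choices (one fixed time, a fixed average, both required) and not under another (either can count, about 6-8% with no true differences). Requiring both keeps the 5% but not the 80% power. The sizes rest on normal changes with SD 3, two-sided tests, the F-test at 5% and the assumed correlation range.

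Three stronger readings are not supported:
- A reader might infer that the trial runs at 10%, or already breaches 5%. The 10% is only the ungated Bonferroni bound, and the plan does not adopt the either-time rule.
- A reader might infer that more patients are needed. Splitting 5% over six tests (0.83% each) would give 73.8% power at 50 per group and need 57 per group. No such split is required, because naming one time or using the gated rule in step 6 controls the error without it.
- A reader might infer that the time will be chosen from the interim data. Section 10.6 plans an interim analysis, but no section says a time would be picked there. The interim analysis and the conflict between 10.8 and 19.7 on stopping are separate matters, to be reconciled on their own, and add no weight here.

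**What to change.** Before any group results are seen, name one primary change, in the same words, in 1.2, 8.2, 8.3 and 10.7. One example is the score immediately after the injection minus the baseline score, stated to be the ANOVA outcome. The 10-minute change or the average of the two would cure the defect equally well; the choice is the investigator's. If a single time is chosen, list the other in 1.3 as secondary. Three comparisons at 1.7% and 50 per group then stand as far as the two times are concerned.

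If both times are to stay primary, write down the rule:
- **Either can count:** F-test at 2.5% per time, pairwise tests at 1.7%, same N. Report power as about 76-80% at any one named time, and about 81% or more for detecting, at one or both times, a difference of 2 points present at both. The 76-80% is not the power of the rule as a whole.
- **Both required:** levels unchanged, same N, power restated as about 66-77%.

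The cost is a few lines of text, with no extra patients, visits or ratings. With one named time, the other becomes supportive only. Separately, and not needed for the error rate, adding the baseline score already collected as a covariate would gain precision at no cost.
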